6.3 Interim Analysis

The protocol stated an interim analysis was planned after the 2 year visit. However due to premature termination of the study no interim analyses will be performed.

7 STATISTICAL ANALYSIS 7.1 General

Smith+Nephew's Global Biostatistics group will conduct the statistical analysis for this study. Unless otherwise stated, all significance tests and hypothesis testing will be two-sided, performed at the 5% significance level. Resulting p-values will be quoted and 95% two-sided confidence intervals will be generated where appropriate. All p-values will be rounded to three decimal places, p-values less than 0.001 will be presented as '<0.001' in all tables.

Where data summaries are specified, categorical and ordinal variables will be summarized with frequencies and percentages. Continuous variables will be summarized with the following summary statistics: number of observations, mean, median, standard deviation, minimum and maximum values. All analyses will be performed in SAS 9.4 (or later).

All table summaries will be provided overall, and by surgical method (resurfaced/un-resurfaced patella).

Example mock shells are provided below:

Table: Demographics by subject				
		Resurfaced Patella	Un-Resurfaced Patella	Overall
Age	Mean			
	Median			
	Std			
	Min			
	Max			
	Q1			
	Q3			
	Inter Quartile Range			
	N			
Age	<65			

CONFIDENTIAL AND PROPRIETARY

Statistical Analysis Plan

Number: Journey II

CR.2020.11 ST: ST1197

Version: V1.0, 20-MAY-

2024

Page: 9 of 20

A Prospective Multi-Centre Study in Patients Undergoing Total Knee Replacement with JOURNEY II CR Total Knee System

>=65		
N		

PROM by knee				
Assessment		Resurfaced Patella	Un-Resurfaced Patella	Overall
Pre-Operative	Mean			
	Median			
	Std			
	Min			
	Max			
	Q1			
	Q3			
	Inter Quartile Ran	nge		
	N			
6 Month				
1 Year				
2 Year				
3 Year				

7.2 Analysis Populations

The following are the analysis populations included in the protocol:

- Safety Population (SAF): This is defined as all subjects who were enrolled and treated with the study devices.
- Intent-to-Treat Population (ITT): The ITT population is defined as subjects from SAF, who have at least one post-operative assessment on any of the effectiveness endpoints.
- Per-Protocol Population (PP): The PP population is a subset of subjects in the ITT population, who do not have major protocol deviations and who satisfied all enrolment eligibility criteria. All major protocol deviations will be formally classified on a case-by-case basis prior to the final study database lock.

However, due to premature termination of the study, all analyses will be performed with SAF population only.

CONFIDENTIAL AND PROPRIETARY

Statistical Analysis Plan

A Prospective Multi-Centre Study in Patients Undergoing Total Knee Replacement with JOURNEY II CR Total Knee System Number: Journey II

CR.2020.11 ST: ST1197

Version: V1.0, 20-MAY-

2024

Page: 10 of 20

7.3 Handling of Missing, Incomplete and Repeat Data

All data will be analysed as observed unless stated otherwise in analysis section.

7.4 Derived Data

Time to Revision:

Time to revision (in months) = (Revision Date - Operative Date)/30.4375.

2011 Knee Society Score (KSS)

The 2011 KSS consists of 34 questions and provides sub-scores across 5 dimensions as shown in Table 4.

Table 4 2011 Knee Society Score

#	Sub-Score	# Questions	Range	Completion by
1	Objective Knee Score	7	0-over 100	Surgeon
2	Subject Satisfaction Score	5	0-40	Subject
3	Subject Expectation	3	3-15	Subject
4	Functional Knee Score	19	0-100	Subject

The Knee Society Score (KSS) comprises information on Objective Knee Indicators (range 0 to over 100 points), Patient Satisfaction (range 0-40), Patient Expectation (range 0-15), and Functional Activities (range 0-100). The KSS endpoints are derived from a series of questions that relate to everyday activities. More elaborate information for deriving the KSS endpoints are described in the publication by Scuderi et al (2012) [1]. However, an abbreviated description of the KSS endpoints used in the study is described in this SAP.

- Objective Knee Score (Completed by Physician/Surgeon)
- The objective score allows for more than 100 points in patients with greater than 125° of flexion and a stable painless knee as outlined below.

CONFIDENTIAL AND PROPRIETARY

Statistical Analysis Plan

A Prospective Multi-Centre Study in Patients Undergoing Total Knee Replacement with JOURNEY II CR Total Knee System Number: Journey II

CR.2020.11 ST: ST1197

Version: V1.0, 20-MAY-

2024

Page: 11 of 20

- "Alignment" allows for a maximum of 25 points and is determined on a weight-bearing AP radiograph measuring the femoral-tibial (Anatomic) axis.
- "Instability" allows for a maximum of 25 points for a knee that is stable in the coronal and saggital axis.
- "Joint Motion" allows one point for each 5° of joint motion with a potential for greater than
 25 points to be assigned for patients with greater than 125° of motion. There are deductions for flexion contracture and extension lag.
- "Instability" has a maximum allowable point allocation of 25+.
- "Symptoms" category contains two 10-level scales, ranging from "none" to "severe" for each patient to rate pain encountered when walking on level ground and on stairs/inclines. For this, a patient starts with 10 points on each scale for a painless knee with deductions of up to 10 points deductions as indicated by the patient's response on each pain scale. There is an additional question regarding how "normal" the knee feels to the patient. The maximum allowable point is 25.
- Patient Expectations and Satisfaction (Completed by Patient)
 - "Patient Expectations" is a three-question fifteen-point scale that is collected pre-operatively
 and post-operatively. The pre-operative questions reflect a patient's opinion on the extent to
 which s/he expects that the operation will improve his/her knee pain, and the ability to
 perform activities of daily living and recreational activities.
 - The post-operative patient expectations questions reflect the extent to which the outcome
 after the operation has met the patient's pre-operative expectations with respect to pain and
 function.

CONFIDENTIAL AND PROPRIETARY

Statistical Analysis Plan

A Prospective Multi-Centre Study in Patients Undergoing Total Knee Replacement with JOURNEY II CR Total Knee System Number: Journey II

CR.2020.11 ST: ST1197

Version: V1.0, 20-MAY-

2024

Page: 12 of 20

- "Patient Satisfaction" is a five-question 40-point scale that is collected preoperatively and at each follow-up visit.
- Functional Score (Completed by Patient)
- The functional score is composed of the four subgroups and has a maximum score of 100 as follows:
 - "Walking and Standing" has a maximum value of 30 points with deductions for the use of walking aids and supports.
 - "Standard Activities" has a maximum of 30 points and evaluates "standard" activities of daily living. Patients can also respond if they never participate in the activities. Patients who respond "I never do this" receive zero points for that activity.
 - "Advanced Activities" has a maximum of 25 points and evaluates function in performing
 more vigorous activities ranging from climbing a ladder or step-stool to running. Patients can
 also respond if they never participate in the activities. Patients who respond "I never do this"
 receive zero points for that activity.
 - "Discretionary Activities" has a maximum of 15 points and allows patients to select the three
 activities that they consider most important to them personally from a group of seventeen
 recreational and exercise activities. Patients who do not participate in any of the
 discretionary activities will have a functional knee score that is limited to 85 points. The
 discretionary activities do not need to be identical in the pre-operative and post-operative
 period.

Forgotten Joint Score (FJS) [2]:

The FJS-12 is a PROM that assesses joint awareness during the activities of daily living. The FJS-12 comprises of 12 questions with a 5-point Likert response format (0 to 4), where 0 = Never; 1 = Never

CONFIDENTIAL AND PROPRIETARY

Statistical Analysis Plan

A Prospective Multi-Centre Study in Patients Undergoing Total Knee Replacement with JOURNEY II CR Total Knee System

Number: Journey II

CR.2020.11 ST: ST1197

Version: V1.0, 20-MAY-

2024

Page: 13 of 20

Almost Never; 2 = Seldom; 3 = Sometimes and; 4 = Mostly. The 12 questions that joint awareness is based on are as follows:

- Night Symptom
- Sitting
- Walking
- Bathing
- Travelling
- Stairs
- Walking uneven ground
- Rising
- Standing
- Housework/Gardening
- Walking/Hiking
- Favorite Sport

An overall score based on the sum of all 12 responses (minimum of 0 and maximum of 48) is computed and transformed linearly into a 0 to 100 score. The higher the transformed score the greater is the ability of the subject to forget about the affected/replaced knee during activities of daily living. If any answer to the above question is missing, the score should not be calculated.

Oxford Knee Score [3]:

In the Oxford Knee score, 12 questions are scored. Each of question is scored in the same way. All questions are laid out similarly with response categories denoting least (or no) symptoms to greatest severity. For example, for question 1:

During the past 4 weeks, How would you describe the pain you usually have from your knee?

CONFIDENTIAL AND PROPRIETARY

Statistical Analysis Plan

Number: Journey II

CR.2020.11 ST: ST1197

Version: V1.0, 20-MAY-

2024

Page: 14 of 20

A Prospective Multi-Centre Study in Patients Undergoing Total Knee Replacement with JOURNEY II CR Total Knee System

The answer and corresponding score are as following:

- None (score as 4)
- Very mild (score as 3)
- Mild (score as 2)
- Moderate (score as 1)
- Severe (score as 0).

The overall score will be calculated by simply summing the scores received for individual questions. This results in a continuous score ranging from 0 (most severe symptoms) to 48 (least symptoms). If there are only one or two questions with no answer, the mean value of all of other responses will be used to imputed. If more than two questions are unanswered, overall score will not be calculated.

Adverse Events

Investigator events do not receive a classification and so S+N classify events as follows:

- An event will be classified as an ADE if the relationship to the study device and/or the relationship to the study procedure is possibly/definitely
- An event will be classified as an SAE if the event is serious
- An event will be classified as an SADE if it is an ADE which is also serious
- An event will be classified as a USADE if it is an SADE which is also unanticipated
- Otherwise, the event will be a non-device, non-procedure related, non-serious AE

For adverse events that have been resolved, duration of adverse event is calculated as end date minus start date

Due to system updates, checks need to be performed to ensure the most stringent classification is being reported. When comparing Investigator assessments (classifications as above) with AEMB classifications, the most stringent classification should be reported as follows:

Investigator	AEMB	Most stringent
assessment	classification	
AE	SAE	SAE
SAE	AE	SAE
AE	ADE	ADE
ADE	AE	ADE
ADE	SADE	SADE
SADE	ADE	SADE

CONFIDENTIAL AND PROPRIETARY

Statistical Analysis Plan

Number: Journey II

CR.2020.11 ST: ST1197

Version: V1.0, 20-MAY-

2024

Page: 15 of 20

A Prospective Multi-Centre Study in Patients Undergoing Total Knee Replacement with JOURNEY II CR Total Knee System

SAE	SADE	SADE
SADE	SAE	SADE
SADE	USADE	USADE
USADE	SADE	USADE

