#### CONFIDENTIAL AND PROPRIETARY

## **Clinical Protocol - Device**

A Prospective Multi-Centre Study in Patients Undergoing Total Knee Replacement Version: 2.0, 02Jun2021 with JOURNEY II CR Total Knee System

Study Number: Journey II CR.2020.11

Page: 24 of 57

Figure 8-1: Study Recruitment Timeline 2020 2021 2025 December October August December EC Submission & **Enrollment** Follow-up

The study is expected to enroll all subjects within a 18 month timeframe. Subjects will be followed-up for a time period of 36 months after surgery. Figure 8-1 details the Study Recruitment timeline. For the study flowchart, please see below Figure 8-2.

This study is being conducted in parallel to another study (which is under same umbrella) titled: "A Prospective Multi-Centre Study in Patients undergoing Total Knee Replacement with Journey II BCS and CR Total Knee System" (Protocol ID: Journey II CR + BCS.2020.12). The study data may be combined for analysis. Further details are described in Statistical Design and the Statistical Analysis Plan (SAP).

Treatment / Enrollment Study Conduct Screening Idendification of potential subject Perform Informed Consent Subject ID shall be assigned Yes Yes Procedure in EDC (RAVE). Perform required study follow-up visits Subject consented? Document on Screening and Document Screening and Enrollment Log Enrollment Log No Document on Screening and Enrollment Log: Subject is considered as Screening Failure

Figure 8-2: Study Flowchart

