## 13.2.1 Ongoing Adverse Events at Study Discontinuation

Adverse events which are related to a study procedure or S+N IP and are ongoing at the end of subject's participation: The event should be followed until it is either resolved or until the event has become chronic and is not expected to further improve based on Investigator's review of the event.

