#### CONFIDENTIAL AND PROPRIETARY

## **Clinical Protocol - Device**

A Prospective Multi-Centre Study in Patients Undergoing Total Knee Replacement Version: 2.0, 02Jun2021 with JOURNEY II CR Total Knee System Page: 45 of 57

Study Number: Journey II CR.2020.11

Adverse events which are **not related** to a study procedure or S+N IP and are ongoing at the end of subject's participation should be followed for 30 days after discontinuation or if the AE is resolved, whichever is sooner.

At the time of data analysis (e.g., interim or final), an evaluation of ongoing events should take place and be listed as ongoing in the safety table.

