7.10 Analysis of Primary Endpoint(s)

The protocol states:

CONFIDENTIAL AND PROPRIETARY

Statistical Analysis Plan

A Prospective Multi-Centre Study in Patients Undergoing Total Knee Replacement with JOURNEY II CR Total Knee System Number: Journey II

CR.2020.11 ST: ST1197

Version: V1.0, 20-MAY-

2024

Page: 17 of 20

The primary endpoint of this study is the OKS at 2 years. If we assume the mean of OKS at 2 years for the subjects with implant JOURNEY II TKA with and without Patella Resurfaced as $\mu 1$ and $\mu 2$. The hypothesis test will be as following:

H0: μ 1 = μ 2 vs

H1: $\mu 1 \neq \mu 2$

The mean difference (μ 1- μ 2) and 95% CI will be estimated. If zero is included in 95% CI of mean difference, then null hypothesis will be accepted, which means patella resurfacing has no impact on the outcomes of JOURNEY II TKA. Otherwise if zero is not included in 95% CI of mean difference, then alternative hypothesis (H1) will be accepted, which means patella resurfacing has significant impact on the outcomes of JOURNEY II TKA. If the lower limit of 95% CI is greater than 0, which means that the subject implant with Patella Resurfaced has higher OKS at 2 years. If the upper limit of 95% CI is less than 0, which means that the subject implant with Patella Resurfaced has lower OKS at 2 years.

In addition, the mean and 95% CI of OKS at 2 years for subjects implant with and without Patella Resurfaced will be estimated separately.

At time of writing the SAP, this study has been early terminated, the study no longer has sufficient power for this hypothesis test to be relevant and it will therefore not be performed. Summary statistics, 95% CI for $\mu 1$ and $\mu 2$ would be presented.

The primary endpoint will be summarized using the SAF population only due to premature termination.

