7.13 Analysis of Safety Endpoint(s)

All safety data will be summarized overall, and by the different surgical methods (resurfaced/unresurfaced).

Adverse event table summaries will be provided using the most stringent classification from Investigator and Adverse Event Monitoring Board (AEMB). Both Investigator and AEMB classifications will be provided alongside the most stringent classification in the Listings.

The number of events and the number of subjects reporting: adverse events (AE) and serious adverse events (SAE), adverse device effects (ADE), serious adverse device (SADE) and unanticipated serious adverse device effects (USADE) will be summarised.

In addition, AEs will be summarised by: frequency, severity, anticipated/unanticipated, relationship to device and procedure; treatment and surgical intervention details (type, reason), outcome and duration of adverse events at trial discontinuation will be summarised.

CONFIDENTIAL AND PROPRIETARY

Statistical Analysis Plan

A Prospective Multi-Centre Study in Patients Undergoing Total Knee Replacement with JOURNEY II CR Total Knee System Number: Journey II

CR.2020.11 ST: ST1197

Version: V1.0, 20-MAY-

2024

Page: 20 of 20

All safety analysis will be performed using the SAF analysis population.

Device Deficiencies

The number of device deficiencies, and the number with potential to cause an SAE will be summarised.

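### AE duration is defined only for resolved events but summarised without that restriction, so in a study stopped early the duration statistic runs short whenever events are still open

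*SAP*

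**What the plan says.** - **Definition (SAP 7.4, Adverse Events):** "For adverse events that have been resolved, duration of adverse event is calculated as end date minus start date". Nothing is said about events that have not resolved.
- **Reporting (SAP 7.13):** "outcome and duration of adverse events at trial discontinuation will be summarised". Safety data are shown overall and by surgical method. The duration summary is not labelled as resolved-only.
- **Missing and incomplete data (SAP 7.3):** "All data will be analysed as observed unless stated otherwise in analysis section". Neither 7.4 nor 7.13 adds an imputed end date or a censoring rule for AEs.
- **Termination (SAP 7.10):** "At time of writing the SAP, this study has been early terminated". The stop date and the follow-up achieved are not given. The planned follow-up was 36 months (Protocol 8.1: "Subjects will be followed-up for a time period of 36 months after surgery").
- **Events open at exit (Protocol 13.2.1):** for related events, "The event should be followed until it is either resolved or until the event has become chronic and is not expected to further improve"; unrelated events "should be followed for 30 days after discontinuation or if the AE is resolved, whichever is sooner". At analysis, "an evaluation of ongoing events should take place and be listed as ongoing in the safety table".
- **Post-exit data (Protocol 13.2):** the sponsor decides whether such added data are documented in the CRF or the study report.

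**The concern.** Whether an event has an end date depends on how long it lasts. At any cut-off, a long event is more likely to be open than a short one with the same onset. Averaging closed events alone therefore selects on the quantity being measured, and the bias is always downward. A shorter observation window makes it worse, and early termination shortens the window. An event that becomes chronic may never receive an end date.

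At stake is how one line of the safety tables is read. The SAP has dropped statistical testing, so descriptive tables are what the study will report. A reader who sees a mean or median duration of adverse events will take it to cover all events, including persistent ones.

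**Working it through.** The documents state no AE duration, AE count or unresolved share, so there is no plan figure to reproduce. The check has two parts.

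**1. What the text produces for an open event.** SAP 7.4 needs an end date, and an open event has none. SAP 7.3 says to analyse as observed, so none is imputed. SAP 7.13 asks for a duration summary all the same. The event therefore contributes nothing to the mean or median. By contrast, SAP 7.11 plans Kaplan-Meier estimates for time to revision, if feasible, with unrevised knees censored at last known follow-up. That treatment is not extended to AE duration.

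**2. How short the statistic could be.** All inputs here are assumptions except the 36-month planned follow-up, used as the longest window:

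- durations are exponential with mean m, from 0.5 to 12 months;
- onset is uniform over a window of T = 12, 24 or 36 months, so the time left after onset is uniform on 0 to T;
- no end date is captured after the window closes.

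With x = T/m:

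- share resolved: p = 1 − (1 − e^(−x))/x
- mean of resolved events: m·[1 − 2/x + e^(−x)(1 + 2/x)] / p

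Example, m = 12 and T = 12, so x = 1: p = 1 − (1 − 0.368) = 0.368. The numerator is 12 × (1 − 2 + 0.3679 × 3) = 1.244. The resolved-only mean is 1.244/0.368 = 3.38 months, and 1 − 3.38/12 = 72% short.

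Results, confirmed by simulation with 2,000,000 events per case. Each cell gives the resolved-only mean in months, the percent short, and the share resolved:

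| True mean (months) | T = 12 | T = 24 | T = 36 |
|---|---|---|---|
| 0.5 | 0.48, 4%, 96% | 0.49, 2%, 98% | 0.49, 1%, 99% |
| 1 | 0.91, 9%, 92% | 0.96, 4%, 96% | 0.97, 3%, 97% |
| 3 | 2.10, 30%, 75% | 2.57, 14%, 88% | 2.73, 9%, 92% |
| 6 | 2.86, 52%, 57% | 4.19, 30%, 75% | 4.82, 20%, 83% |
| 12 | 3.38, 72%, 37% | 5.72, 52%, 57% | 7.31, 39%, 68% |

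The median moves the same way. For a true mean of 12 months the true median is 8.32 months, and the resolved-only median is 2.78, 4.46 and 5.50 months at T = 12, 24 and 36.

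**A mix of events.** Take 85% short events (mean 1 month) and 15% long ones (mean 18 months). The true mean is 0.85 × 1 + 0.15 × 18 = 3.55 months. The resolved-only mean is 1.04, 1.37 and 1.68 months at T = 12, 24 and 36. The median is much less affected: 0.67, 0.73 and 0.76 against a true 0.87.

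**Two further results bear on the fix.**

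- Using the cut-off as if it were the end date does not repair the mean. For a true mean of 12 months it gives 4.42, 6.81 and 8.20 months.
- Total observed time divided by resolved events returns the true mean in the exponential cases. In the mix it gives only 1.84, 2.30 and 2.59 against 3.55. A Kaplan-Meier median, which assumes no duration distribution, is therefore the safer summary.

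**The case against.** **Exclusion is inferred.** SAP 7.4 never says that ongoing events are left out; it is silent on them. The phrase about trial discontinuation in SAP 7.13 might even mean elapsed time at that point. This is fair as a reading of the words. But no formula supports the alternative, and a programmer who has only 7.3 and 7.4 has nothing to compute for an open event.

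**Ongoing events stay visible.** A reader might infer that persistent problems vanish from the safety report. The documents do not support that. SAP 7.13 counts all AEs by class, summarises them by severity, relationship, treatment and outcome, and provides listings. Protocol 13.2.1 has ongoing events shown as ongoing in the safety table. Only the duration statistic is affected.

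**Follow-up continues after exit.** Under Protocol 13.2.1, related events are followed until resolved or chronic, and unrelated ones for up to 30 days. The calculation above assumes a hard cut-off, so it overstates the loss if those end dates are entered. They may not be, because Protocol 13.2 leaves documentation to the sponsor and the SAP does not say whether such dates are used.

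**The comparison between surgical methods.** A reader might infer that the group with shorter follow-up loses more events, so that durations cannot be compared. That would need unequal follow-up. No section reports follow-up by group, and both groups share one enrolment window and one visit schedule. Non-random allocation makes a difference possible but does not show one.

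**Same-day events score 0 days.** This is a convention. Adding one day would shift every duration equally, and SAP 7.4 uses a plain date difference for time to revision too.

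**Proportion.** AE duration is not a listed safety endpoint in SAP 5.3 and feeds no test. Events open at cut-off also include recent-onset short ones. Both points stand and keep this minor.

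**Conclusion.** The point holds as a minor reporting defect. SAP 7.4 conditions the duration calculation on resolution, SAP 7.13 reports duration without that condition, and no rule covers ongoing events. The resulting statistic is short whenever any events are open.

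The direction follows from the rule, but the size does not. It depends on the unresolved share and the observation window, neither of which the documents give. Under exponential durations, uniform onset and a hard cut-off at 12 to 36 months, the shortfall in the mean is about 1–9% for AEs averaging one month or less and about 39–72% for AEs averaging 12 months. If nearly all AEs resolve quickly, or if post-exit end dates are captured, the effect is negligible. No primary result, AE count or outcome summary is affected.

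**What to change.** In SAP 7.4 and 7.13:

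- **Preferred:** keep the present date difference for resolved events and treat ongoing events as censored at last contact or data cut-off. Report a Kaplan-Meier median time to resolution overall and by surgical method, with the numbers resolved and ongoing. Describe it as descriptive and at event level. Where the median is not reached, say so.
- **Minimum:** title the statistic *duration of resolved AEs*. Beside it, show by surgical method the number and percent ongoing, with their elapsed times given as *at least* durations.
- **Either way:** state the cut-off date, and whether end dates obtained after a subject's exit under Protocol 13.2.1 are used.

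The cost is a little more programming and no new data. One limitation should be noted in a footnote: event-level Kaplan-Meier treats several events in one subject as independent, and treats death with an event still open as ordinary censoring. For a descriptive table that is acceptable if stated.
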